1.1 Funding

NSW Health is funding the development, implementation, and monitoring of the trial through a grant awarded to a consortium of universities and academics led by Chief Investigator, [name] from the University of Newcastle, titled NSW Government-Sponsored Clinical Trial: Management of Urinary Tract Infections by Community Pharmacists to include oral contraception and management of minor skin conditions. This protocol is to undertake the Intervention study for oral contraception.

1.5 Glossary of abbreviations and terms

APDC	Admitted Patient Data Collection	
CFIR	Consolidated Framework for Implementation Research	
ED	Emergency Department	
EDDC	Emergency Department Data Collection	
EPA	Extended Practice Authority	
GDS	George Data Systems	
GP	General Practitioner	
HREC	Human Research Ethics Committee	
ID	Identification	
MBS	Medicare Benefits Schedule	
MMM	Modified Monash Model	
NPT	Normalisation process theory	
NSW	New South Wales	
00	Oral Contraception	
OCP	Oral Contraceptive Pill	
PSA	Pharmaceutical Society of Australia	
PBS	Pharmaceutical Benefits Scheme	
SEIFA	Socioeconomic indexes for area	
TGI	The George Institute for Global Health	
UoN	University of Newcastle	

2. Protocol Synopsis

On 19 February 2023, the NSW Government announced that its pharmacy prescribing trial would be expanded to include the provision of the oral contraceptive pill (OCP) for women 18-35 years.

The overall aim of this study is to evaluate the clinical and economic impact and implementation of a service model (intervention) delivered by community pharmacists in NSW and 5 pharmacies in ACT, re-supplying specific oral contraceptive pills for a specific patient cohort over a 12-month study period. Women must be aged between 18 to 35 years (inclusive), taking the pill for contraception purposes only, and has seen their GP/nurse practitioner for a review of their low-risk oral contraceptive pill in the last two years.

The specific objectives of this study are to:

- 1. Assess the accessibility and acceptability for patients managed and/or supplied a low risk contraceptive pill by community pharmacists.
- 2. Assess implementation uptake of the intervention including the reach, fidelity and adoption of the intervention in community pharmacies, participant characteristics, and variation in uptake by geographic region.
- 3. Assess the clinical outcomes and patient experience for patients managed by community pharmacists.
- 4. Assess the safety of the intervention and identify any risks that need to be addressed for future implementation.
- 5. Qualitatively assess the acceptability and feasibility of the intervention to pharmacists, other care providers and participants using the service.
- 6. Identify contextual enablers and constraints to access, adoption, fidelity delivery, impact, sustainability, and generalisability of the intervention.
- 7. Conduct a health economic evaluation to determine the economic benefits.

The study will use a cohort study design to assess the clinical and economic and implementation of the intervention in NSW and ACT over a 12-month study period. The intervention is multicomponent including Pharmacist training and support and a Pharmacy consultation, using an IT program, applying one of two clinical management protocols. Pharmacies and pharmacists must meet the criteria of an 'approved pharmacist' outlined in the NSW Health Authority, or a licence in ACT, to participate.

Primary outcomes will be accessibility and acceptability of the service (based on self-report at 7-day follow up). This will be a composite measure based on patient self-reported data. It includes seven items adapted from existing questionnaires, including a validated questionnaire for perceived service quality in community pharmacies (two items) and studies of pharmacy prescribing for oral contraception, and other medications [1-6]. It will cover the following domains: (a) trust and confidence in health and medical advice provided, (b) convenience, (c) privacy during discussion with pharmacy, and (d) overall satisfaction. Each item is scored on a 7-point Likert scale. Each domain will be equally weighted, and an aggregated score calculated and scaled to a maximum score of 100. Semi-structured interviews with pharmacists and other stakeholders will be conducted to better understand barriers and facilitators to implementation of the service.

3. Introduction

3.1 Background to community pharmacy prescribing

On an international and national basis, the scope of practice for community pharmacists is evolving rapidly. The NSW and ACT Governments have recognised this expanded role community pharmacists could play. The broad approach is to increase the community's access to primary care through:

- 1. Authorising pharmacists to administer a wider range of public health and travel vaccinations from 14 November 2022, including Japanese Encephalitis, Hepatitis A and Hepatitis B, Poliomyelitis, Typhoid and Zoster.
- 2. Funding a 12-month trial to evaluate allowing pharmacists to manage uncomplicate urinary tract infections in a specified cohort of females.
- 3. Funding a 12-month trial to evaluate allowing pharmacists to extend the supply of certain low risk oral contraceptive pills (OCPs).
- 4. Supporting a state-wide trial where appropriately trained pharmacists can prescribe medications for certain conditions, such as skin ailments [7].

This study protocol refers to the third goal above.

Contraception plays a pivotal role in the well-being and health of women permitting individuals control over their sexuality, fertility, and reproductive choices [8]. The public health and development impact of contraception is well established and so profound that access to contraception is now considered an essential element of the human right to health in the international community [8]. Contraception improves birth outcomes, slows population growth, and improves socioeconomic status [8]. Despite the proven effectiveness and benefits of contraception, advances in contraceptive technology, and the recognition of contraceptive access as a basic human right, the international community is said not to have achieved universal access to contraception [8].

Barriers to access are one reason for inconsistent or non-use of contraception [9, 10]. There are several barriers such as the requirement for a prescription that can prevent women from continuing their contraceptive method of choice [10]. As stated in The Senate Community Affairs References Committee; Ending the postcode lottery: Addressing barriers to sexual, maternity and reproductive healthcare in Australia (May 2023), other key reported obstacles include: regulatory restrictions limiting the role of pharmacists, inadequate incentives for medical practitioners to bulk-bill, contraceptives not available on the PBS, high financial costs, and limited access in rural and remote regions and First Nations communities [10].

Expanding access to contraception allows individuals to safely space and limit their pregnancies and reduces unintended pregnancies, maternal morbidity and mortality [8, 10]. It is accepted at an international level that there is significant potential to increase access to prescription contraceptives in a cost-efficient manner by expanding the scope of practice among a range of allied health professionals, including pharmacists, who with the appropriate training, could help provide contraceptive care [11]. Studies have established that women can self-screen and non-physicians can safely assess for medical contraindications to OCP use [12-16].

Authorising pharmacists to facilitate the continuation of oral contraception in community pharmacy has been shown to be an effective strategy that can increase access to contraception [17]. There is evidence from several countries that suggests pharmacists are well positioned to facilitate the initiation and continuation of hormonal contraception in certain cohorts within the community pharmacy setting. It has become usual practice in some states of the USA [18-28], several regions of the UK [29-32], some provinces in Canada, and New Zealand [33]. Pharmacist supply and continuation of OC offers several advantages, including the alleviation of logistical challenges such as time for appointments, scheduling difficulties, and costs [17]. In addition, pharmacist supply for continuation of contraception can increase access to contraceptives through offering more convenient locations, extended hours of operation, and ability to avoid gaps in medication use when away from home [10, 17]. It is widely believed that since consumers do not require an appointment and pharmacies have expanded hours and locations, direct OCP access through pharmacies may improve contraceptive continuation rates over the traditional standard of care pathway, which requires a clinic visit with a physician or advanced practice clinician [12]. Improving continuation rates may also minimises the risks associated with non-continuance VTE risk.

Moreover, as previously stated by enhancing accessibility to contraceptives, this approach has the potential to effectively decrease unintended pregnancies. It is estimated that one in four Australian women experience an unintended pregnancy during their lifetime, with rates even higher in non-urban areas [10]. Unintended pregnancies are defined as either mistimed (pregnancy occurs earlier or later than desired) or unwanted (pregnancy occurs when no or no more children are desired) [10, 34]. Unintended pregnancies can place

significant physical, social and financial strains on women and their families [10]. This is a major health issue and an area of unmet demand for Australian women [10].

In the Australian context, the NSW and ACT Government have committed to examining the impact of the supply of low-risk oral contraceptive pills to eligible women by community pharmacists under a trial framework to capture robust outcome data to inform the future scope and role of community pharmacists. The implementation of a large-scale trial across NSW (and 5 pharmacies in the ACT) will assist the State Government in better understanding the impact of the service for a specific patient cohort [35].

3.2 Aim and objectives

3.2.1 Aim

The overall aim of this study is to evaluate the clinical and economic impact and implementation of a service model (intervention) delivered by community pharmacists in NSW and 5 pharmacies in ACT, re-supplying specific oral contraceptive pills for a specific patient cohort over a 12-month study period. Women must be aged between 18 to 35 years (inclusive), taking the pill for contraception purposes only, and has seen their GP/nurse practitioner for a review of their low-risk oral contraceptive pill in the last two years.

3.2.2 Objectives

Specific objectives are to:

- 1. Assess the accessibility and acceptability for patients managed and/or supplied a low risk contraceptive pill by community pharmacists.
- 2. Assess implementation uptake of the intervention including the reach, fidelity and adoption of the intervention in community pharmacies, participant characteristics, and variation in uptake by geographic region.
- 3. Assess the clinical outcomes and patient experience for patients managed by community pharmacists.
- 4. Assess the safety of the intervention and identify any risks that need to be addressed for future implementation.
- 5. Qualitatively assess the acceptability and feasibility of the intervention to pharmacists, other care providers and participants using the service.
- 6. Identify contextual enablers and constraints to access, adoption, fidelity delivery, impact, sustainability, and generalisability of the intervention.
- 7. Conduct a health economic evaluation to determine the economic benefits from the intervention.

4. Methods

4.1 Study hypothesis

The study hypothesis is that an intervention (OCP service) delivered by community pharmacists for women 18-35 years will be acceptable to participants and providers, accessible, cost-effective and not associated with increased safety risks.

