4.2 Study design

The study hypothesis will be tested using a cohort study design, applying mixed methods (quantitative and qualitative research) to assess clinical and economic indicators, implementation, and patient experience.

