4.3 Pharmacy recruitment

This state-wide study and as part of the contract with the NSW Government, the researchers are obliged to include any approved pharmacy and approved pharmacist in NSW that request participation. Furthermore, as part of the Contract with NSW Health, we have agreed to include 5 pharmacies in the ACT.

In the first instance, the NSW Ministry of Health created an expression of interest (EOI) form on their website (https://www.health.nsw.gov.au/pharmaceutical/Pages/community-pharmacy-pilot.aspx) to which pharmacies were encouraged to complete if interested in participating. Similarly, the Pharmacy Guild of Australia (NSW Branch) and Pharmaceutical Society of Australia (NSW Branch) completed a similar process in seeking EOIs to participate in the research. Details were forwarded to the research team with consent. Pharmacies who submitted an expression of interest were assessed to ensure they meet the eligibility criteria for the project.

NSW pharmacies

The contractual arrangements with the NSW Ministry of Health oblige us to offer participation to all New South Wales pharmacies who had consented to the previous trial (UTI) (ACTRN12623000882628). A formal recruitment letter will be sent via email to those 1109 pharmacies who had already previously consented, including the Participant Information Sheet and Consent forms for both Pharmacy and Pharmacist requesting involvement to be signed and returned electronically (Appendix 5-12). Consent will be sought at the pharmacy level from pharmacy owners, and from the individual pharmacists in those pharmacies consenting to participate in the study.

Pharmacies will be sent Participant Information Sheet and Consent forms electronically via DocuSign and have requested individuals to accept the invitation after 10 days. Pharmacies who do not consent in the timeframe will be sent a follow up, 10 days after the initial invitation. For pharmacies/pharmacists who indicate via email they would like further information or clarification, a follow up email and/or phone call will be made by a member of the research team using a standardised script (Appendix 13).

ACT pharmacies

As per the process in NSW, the 5 participating pharmacies in ACT, which were previously randomly selected to ensure a geographic spread of participation across regions, will be sent a formal recruitment letter including the Participant Information Sheet and Consent forms for both Pharmacy and Pharmacist was sent.

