4.6.2 Participant (patients) self-reported data

Participants will be assessed at the registration visit (consultation) described above and this will include basic demographic and clinical information. Those assessed as eligible to participate in the trial will be followed up at Day 7 post registration to assess outcomes. This will include a brief survey administered by the George Institute either via SMS message or phone call with a link to a case report form using George Data Systems (GDS). Appendix 19 provides the case report form for the 7-day follow-up visit.

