4.9 Outcomes

Primary outcomes

Primary outcomes will be accessibility and acceptability of the service (based on self-report at 7-day follow up). This will be a composite measure based on patient self-reported data. It includes seven items adapted from existing questionnaires, including a validated questionnaire for perceived service quality in community pharmacies (two items) and studies of pharmacy prescribing for oral contraception, and other medications [1-6]. It will cover the following domains: (a) trust and confidence in health and medical advice provided, (b) convenience, (b) privacy during discussion with pharmacy, and (b) overall satisfaction. Each item is scored on a 7-point Likert scale. Each domain will be equally weighted, and an aggregated score calculated and scaled to a maximum score of 100.

Secondary outcomes

- **On time dispensing rates**: 36 months pre and 12 months post introduction of the intervention (assessed using the proportion of days covered method using PBS data) [40].
- **Primary care utilisation:** MBS records will be used to measure use of general practice services prior up to 36-months pre and 12 months post introduction of the intervention date (MBS data).
- **Safety outcomes**: Adherence rates to Clinical management protocols (assessed by practice change facilitators conducting regular pharmacy monitoring and inspection of data from the patient consultation IT system), hospitalisation for potential pill-related adverse events (e.g., thromboembolic disease) (NSW Health data), rates of STI tests undertaken (MBS pathology data) and adverse events.
- **Implementation outcomes**: Implementation outcomes will also be assessed to examine the fidelity, reach and adoption of the new service, and barriers and facilitators to implementation.

• **Economic outcomes:** Results from the economic analysis will be expressed as (1) net benefit in terms of implementation costs and cost savings arising from more efficient treatment pathways; and (2) cost-consequence results accounting for patient experience measures, relevant safety outcomes and implementation measures. This will be assessed using multiple data sources including MBS records for 36 months pre and 12 months post introduction of the intervention.

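### The hypothesis claims no increase in safety risk, but the single-arm design gives the safety outcomes and the primary score nothing to be compared with

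*Protocol*

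**What the plan says.** Protocol section 4.1 states that the service "will be acceptable to participants and providers, accessible, cost-effective and not associated with increased safety risks". Section 4.2 adds: "The study hypothesis will be tested using a cohort study design". No comparison group is described anywhere in the protocol.

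Section 4.9 sets the outcomes:

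- **Primary.** "Primary outcomes will be accessibility and acceptability of the service (based on self-report at 7-day follow up"). Seven items cover four domains: trust, convenience, privacy and overall satisfaction. "Each domain will be equally weighted, and an aggregated score calculated and scaled to a maximum score of 100".
- **Safety.** Pharmacists' adherence to the management protocols, "hospitalisation for potential pill-related adverse events (e.g., thromboembolic disease) (NSW Health data"), STI testing and adverse events. Nothing is said about what these are to be compared with.
- **Other secondary outcomes.** On-time dispensing, GP use and the economic outcomes are given windows of 36 months before and 12 months after the service. Section 4.6.5 adds discontinuation before and after.

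Section 4.7.5 obtains hospital records through NSW Health, from 12 months before registration onward. On the ACT, section 4.3 says "we have agreed to include 5 pharmacies in the ACT". Section 4.10.3 defines the economic results as a net benefit, with bootstrap uncertainty intervals, and a cost-consequence account.

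**The concern.** Whether risk has increased is a comparative question. It needs a rate expected without the service, or a concurrent group, and a margin for what counts as no increase. The safety outcomes have none of these, so a low count of hospitalisations could be reported as confirming the hypothesis when it shows only that few events were seen. The regression models in 4.10.1 do not help: adjusting for age, comorbidity, prior primary care use and area disadvantage describes variation among users of the service, not a difference from non-use.

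The primary score has a similar gap. It is taken once, after the service, from women who used it, with no comparison value. It can describe their experience, but it cannot show that access improved or how women who did not reach the service would fare.

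Section 3.1 says the trial is meant to inform the future role of community pharmacists, so a safety conclusion that the design cannot support would carry weight.

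**Working it through.** **Step 1. Match each term of the hypothesis to its reference.**

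| Term in 4.1 | Outcome bearing on it | Reference stated |
|---|---|---|
| Acceptable, accessible | Day-7 composite (4.9) | None |
| No increase in safety risk | Protocol adherence, pill-related hospitalisation, STI tests, adverse events (4.9) | None |
| Cost-effective | Net benefit, cost-consequence (4.10.3) | MBS, 36 months before and 12 after |
| Not named in 4.1 | Dispensing, discontinuation, GP use (4.6.5, 4.9) | Before and after the service |

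**Step 2. Can the existing pre-periods serve for safety?** Section 4.4.2 requires two continuous years of stable use of the same pill. So 24 of the 36 pre-service months fall where continuation is a condition of entry, and dispensing before entry is selected to look good. The 12 months of earlier hospital records lie wholly inside that stretch. A woman whose pill was stopped after a related admission in that year would not qualify, so the earlier rate is probably too low as a reference. The protocol does not in any case plan that contrast.

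**Step 3. What could an event count show?** The protocol gives no cohort size, event rate or margin, so there is no planned figure to reproduce. Everything in this step rests on assumed values, with one year of follow-up per woman.

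With zero events, the one-sided 95% upper limit is −ln(0.05)/N:

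- N = 1,000: 2.996/1,000 = 30 per 10,000 woman-years
- N = 5,000: 2.996/5,000 = 6 per 10,000
- N = 20,000: 2.996/20,000 = 1.5 per 10,000

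To detect a doubling against a fixed reference rate r, let m = r × N. Take the smallest c with P(X ≥ c | m) ≤ 0.05; power is P(X ≥ c | 2m), with X Poisson. For r = 10 per 10,000 and N = 5,000: m = 5, c = 10, and P(X ≥ 10 | 10) = 0.54. The before-and-after columns use an exact conditional binomial test of 12 against 12 months, one-sided 5%.

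| Assumed rate per 10,000 | Fixed reference, N = 5,000 | Fixed reference, N = 20,000 | Before/after, N = 5,000 | Before/after, N = 20,000 |
|---|---|---|---|---|
| 2 | 0.14 | 0.41 | 0.02 | 0.22 |
| 5 | 0.38 | 0.84 | 0.12 | 0.51 |
| 10 | 0.54 | 0.97 | 0.28 | 0.80 |
| 20 | 0.84 | 1.00 | 0.51 | 0.98 |

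The answer runs from almost no information to near certainty, depending on inputs that the protocol does not give.

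**Step 4. ACT share of pharmacies.** Section 4.3 gives 1,109 NSW pharmacies invited and 5 in the ACT.

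- All NSW pharmacies join: 5/1,114 = 0.45%
- Half join (assumed): 5/(554.5 + 5) = 0.89%
- One in ten join (assumed): 5/(110.9 + 5) = 4.31%

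**Step 5. Weight of convenience.** It is one of four equal domains, so 25%. A participant scoring it 1 of 7 and everything else 7 of 7 has a domain mean of (1 + 3 × 7)/4 = 5.5. That is (5.5 − 1)/6 × 100 = 75 on a 0–100 rescaling, or 5.5/7 × 100 = 79 as a percentage of the maximum. This profile is extreme, but it shows that the composite alone can hide poor convenience.

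**The case against.** The strongest reply is that the study does have comparators and can produce unfavourable results. A reader might infer from 4.1 and 4.2 that nothing is compared with anything and that a favourable conclusion could never be refuted. The documents do not support that. Dispensing, discontinuation, GP use and MBS-based economics are compared with a pre-service period. The net-benefit interval can fall below zero. Under 4.11 the DSMB weighs risk against benefit and may recommend changing or stopping the study. Section 4.10.3 itself concedes that the cohort design constrains the cost analysis. All of this stands, and it confines the point to the safety outcomes and the primary score.

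Other replies also have force. Day 7 is a reasonable time to ask about a consultation, and hospitalisation rests on linked records, not on that survey. Access is also approached through reach and regional uptake (3.2.2, 4.9) and through travel and waiting time (4.10.3). Equal domain weights are a legitimate choice, and the item scaling may sit in an SAP that is not shown. Benchmarks may sit there too, but a comparison group is a matter of design and none is described here.

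A reader might also infer that ACT participants will be counted as event-free. The protocol does not say that they enter the hospitalisation denominator; it only provides no ACT hospital source.

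**Conclusion.** The point holds in limited form. The safety claim in 4.1 is comparative, the safety outcomes in 4.9 have no stated reference, and the primary score has no comparator. Few or no events would bound the rate but would not show that risk is unchanged. The pre-periods that exist belong to other outcomes and are selected by the two-year stability rule.

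The numerical size is conditional. The 5,000 and 20,000 woman-years and the rates of 2 to 20 per 10,000 are assumptions used to show the range; none comes from the protocol, and the protocol plans no such test.

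The term cost-effective is a lesser matter of wording: the analysis yields net benefit and cost-consequence results and should be named accordingly. The ACT gap is minor, at 0.45% of invited pharmacies and about 4% only if NSW uptake were as low as one in ten. That assumes pharmacies recruit similar numbers of women.

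**What to change.** 1. In 4.1 and 4.2, state that safety will be estimated, not tested.
2. In 4.9 and 4.10.1, report pill-related hospitalisation per woman-year with an exact Poisson one-sided 95% upper limit, with NSW participants only in the denominator. ACT participants can stay in the survey, MBS and PBS outcomes.
3. State that few or no events will not be read as showing no increase in risk.
4. In 4.1, replace the cost-effectiveness claim with the net-benefit and cost-consequence results that 4.10.3 defines.
5. Keep the composite as the primary outcome, report the convenience domain separately beside it, and limit any survey-based claim about accessibility to women who used the service.
6. Where before-and-after results are reported, note that the two-year stability criterion selects the earlier period.

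The cost is wording in 4.1, 4.2, 4.9 and 4.10, plus one extra reported score. No new data collection is needed. The drawback is a weaker headline: the trial could report a rate and its upper limit, but could not claim that risk is unchanged.
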